7. STUDY PROCEDURES

7.1. Recruitment

Consecutive admitted patients will be assessed for inclusion and exclusion criteria by a research physician. If eligible, the participant will be enrolled in the study. Details of those fulfilling the entry criteria will be entered onto a screening form, while reasons for non-eligibility will be added to the eligibility-screening log. It is expected that this process will take approximately 30 minutes.

7.2. Informed consent

No ethical concern is attributable to this study due to its observational nature. No direct intervention on patient is part of the study design. Personal information (name, age, community, etc.) from registries will be anonymized and no patients will be recognizable during the realization or dissemination phases of the study. Serial ultrasound examinations are standard of care in obstetric patients, while lung ultrasound is routine practice in intermediate and intensive care units, especially in the absence of alternative image modalities as chest radiography or computed tomography. For these reasons, a waiver of patient individual informed consent is requested to this EC. Sharing of patient data will follow Good Clinical Practice guidelines and ethics review committee advice.

7.3.1. Screening demographic and medical history

Basic demographic and epidemiological data (i.e. age, sex, medical history of hypertension disease) will be obtained to assess eligibility and recorded in the screening log by the study staff.

7.3.2. Screening physical exam and vital signs

Vital signs will be conducted by a research physician including Glasgow Coma Scale (GCS), pulse rate, blood pressure, respiratory rate, aural temperature (average of left and right ears), and pulmonary auscultation. The screening vital signs will be recorded in the screening log by the study staff.

7.4. Baseline Assessments

Following screening and eligibility confirmation the baseline assessments will be performed as detailed below. The duration of time to perform baseline assessment will take approximately 1 hour.

7.4.1. Demographic and medical history

A detailed demographic, epidemiologic (i.e. age, sex, address, previous medications) and past-medical history will be obtained and recorded in the Case Report Form (CRF) by the research staff. All prescribed or over-the-counter drugs, traditional medications and any drug allergies will also be recorded.

7.4.2. Physical exam and vital signs

Upon enrolment, a full physical examination will be conducted by a research physician. Vital signs including GCS, pulse rate, blood pressure, respiratory rate, SpO₂, FiO₂, aural temperature (average of left and right ears), weight, height and a neurological exam will be recorded in the CRF.

7.4.3. Non-invasive investigations

Baseline investigations will include echocardiography and lung ultrasound. Briefly, point-of-care ultrasonography will include: (1) lung ultrasound following a 12-region protocol, (2) echocardiography.

8. INVESTIGATIONS

8.1. Ultrasound Examinations

8.1.1. Lung ultrasound examination

A complete 12-region lung ultrasound examination will be conducted with a standard ultrasound machine and a low frequency (2.5–5MhZ) convex probe. The ultrasound machine, the probe and the probe holder will be cleaned before and after each use using the dedicated antiseptic detergent indicated by hospital guidelines. The patient remains in supine position and the probe will be held perpendicular to the skin. Briefly, the 12-rib interspaces will be scanned at the bedside with the ultrasound probe applied longitudinally and perpendicularly to the exterior chest wall. The left and right hemi thorax will be assessed in six areas: two anterior areas, two lateral areas, and two posterior areas. The anterior chest will be delineated as the parasternal to the anterior axillary line and divided into upper and lower halves (zones 1 and 2). The lateral area will be delineated as the anterior to the posterior axillary line and divided into upper and basal halves (zones 3 and 4). The posterior area will be considered as the zone beyond the posterior axillary line and divided into upper and lower zones (zones 5 and 6). The lung ultrasound score (sum of patterns found on each scanning site) will be recorded (score 0: pattern with less than three Blines; score 1: Three or more separated B lines; score 2: multiple and confluent B-lines; score 3: consolidation) (36). The global lung ultrasound score will range from 0 to 36. Additional ultrasound findings include the assessment of subpleural consolidations, pleural effusions and lung sliding.

8.1.2. Cardiac echocardiographic examination

In the supine position, bedside images will be obtained using a with a low frequency (2.5-5 MhZ) sector cardiac probe. Focused echocardiographic examination will include two windows of the exterior chest wall: the parasternal long axis (PLAX) and the 4-chamber long views (4CLV). The cardiac ultrasound will obtain the real-time assessment of maternal cardiac contractility and cardiac output.

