4. OBJECTIVES AND OUTCOME MEASURES

Objectives	Outcome Measures	
Primary objective		
To describe the frequency of LUS abnormalities consistent with pulmonary oedema	Frequency endpoint: proportion of patients with LUS consistent with pulmonary edema Severity endpoint: LUS aeration score (numerical 0 to 36)	
To describe the timing and entity of edema resolution after delivery	Frequency endpoint: Fraction of patients with improvement or resolution of LUS findings. Quantitative endpoint: delta LUS score between T1 and T2	
Secondary objectives: To describe the frequency of acute respiratory failure in patients with Severe Pre- eclampsia and in patients with Eclampsia	Proportion of patients with acute respiratory failure (see definition)	
Frequency of other LUS findings	 Proportion of patients with: consolidations isolated pleural effusion minor LUS findings Calculation of the LUS ARDS score 	
Frequency of organ support strategies	Fraction of patients that receive: - oxygen - CPAP - Mechanical ventilation	
Frequency of patients with abnormal cardiac function	Defined as either low cardiac output measured by ultrasound	
Oxygenation assessment	SpO ₂ to FiO ₂ ratio	
Frequency of Major Direct Obstetric Complications	Fraction of patients with at least one additional MDOC (APH, PPH, sepsis, uterine rupture, obstructed labour)	
Frequency of Indirect Obstetric complications	Fraction of patients with at least one among stroke, severe malaria, acute kidney injury and cardiac insufficiency	
Frequency of perinatal complications	IUFD, Apgar score, Admission to special care baby unit (SCBU)	

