5. STUDY DESIGN

This will be a single centre, prospective, cohort study of patients with severe pre-eclampsia and eclampsia. The expected duration of study is 1 year. All patients with suspected severe pre-eclampsia or eclampsia will undergo screening upon admission to HDU and the Eclamptic ward. Eligible patients will undergo a systematic clinical and LUS examination, straight after admission (**before delivery**). Clinical examination will focus on signs of respiratory, neurologic and cardiac failure. Lung ultrasound will be performed using a MyLab[™]Five ultrasound machine (Esaote Spa, Genova, Italy) and a low frequency (2.5–5 MHz) convex probe or a Butterfly ultrasound probe (Butterfly, USA). Lung ultrasound will be performed using the

validated 12-region method, evaluating 2 anterior regions, 2 lateral regions and 2 posterior in each hemithorax (18,28,29). As heart failure is a common finding in preeclamptic women, echocardiography performed with a cardiac sector probe, will enable real-time assessment of maternal cardiac contractility and cardiac output. The same clinical, LUS and echocardiographic assessment will be repeated between 24 h to 72 h (after delivery). Whenever the pre-delivery timepoint is not feasible due to late arrival, emergency scenario or postpartum onset, the after delivery examination only will be performed.

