Chest imaging	Bilateral opacities not fully explained by effusions, lobar/lung collapse, or nodules by chest radiograph or CT	Bilateral opacities not fully explained by effusions, lobar/lung collapse, or nodules by chest radiograph or ultrasound
Origin of oedema	Respiratory failure not fully explained by cardiac failure or fluid overload (need objective assessment, such as echocardiography, to exclude hydrostatic oedema if no risk factor present)	

Table 1. Berlin Criteria for ARDS and Kigali Modification of the Berlin Criteria (19,32)

Bilateral opacities on ultrasound will be defined as two or more regions with a B-pattern and/or C-patterns per hemithorax bilaterally (33).

Abbreviations: ARDS, acute respiratory distress syndrome; PaO2, arterial oxygen tension; FiO₂, fraction of inspired oxygen; SpO₂, oxygen saturation as measured by pulse oximetry; AECC, American-European Consensus Conference; CT, computed tomography; PEEP, positive end-expiratory pressure.

Abnormal cardiac function

Defined as a cardiac index (CI) <2.5 l/min/m2 measured by echocardiography.

Modified Early Warning (MEWS) Score

The modified early warning score ranges from 0 to 14 and is calculated as detailed in **Table 2** (34) (35).

Physiological parameters	Normal values (0 points)	Yellow alert (1 point)	Red Alert (2 points)
Respirator rate	10- 20 breaths pwe minute	21- 30 breaths per minute	<10 or >30 breaths per minutes
Oxygen saturation	96- 100%		<95%
Temperature	36.0- 37.4°C	35- 36 or 37.5- 38°C	<35 or >38°C
Systolic blood	100- 139 mmHg	150- 180 or 90- 100	>180 or < 90 mmHg
pressure		mmHg	
Diastolic blood	50- 89mmHg	90- 100 mmHg	>100 mmHg
pressure			
Heart rate	50- 99 beats per		>120 or <40 beats per minutes
	minute	100- 120 or 40- 50	
		beats per minute	
Neurological	Alert	Voice	Unresponsive, pain
response			

Table 2. The Modified Early Warning Score score.

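### Echocardiographic cardiac output is acquired supine before delivery and judged against one fixed cut-off with no time point named, so the frequency of abnormal cardiac function can be inflated by position in women scanned while pregnant

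*Combined protocol and SAP*

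**What the plan says.** Section 8.1.2 fixes the position for the cardiac scan, "In the supine position, bedside images will be obtained", and says what the scan is for: "The cardiac ultrasound will obtain the real-time assessment of maternal cardiac contractility and cardiac output".

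On timing, section 5 places the first assessment before delivery: "Eligible patients will undergo a systematic clinical and LUS examination, straight after admission". That sentence does not name echocardiography, but section 7.4.3 does: "Baseline investigations will include echocardiography and lung ultrasound". Section 5 then adds: "The same clinical, LUS and echocardiographic assessment will be repeated between 24 h to 72 h", counted from delivery. Some women skip the first scan, "Whenever the pre-delivery timepoint is not feasible due to late arrival, emergency scenario or postpartum onset", and have the after-delivery examination only. Their expected number is not given.

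On the outcome, section 6.4 gives one absolute threshold: "Defined as a cardiac index (CI) <2.5 l/min/m2 measured by echocardiography". The objectives table in section 4 lists the frequency of abnormal cardiac function as a secondary outcome, "Defined as either low cardiac output measured by ultrasound", while the synopsis speaks of cardiac index. None of the three places says whether the outcome is counted before delivery, after delivery or at either scan.

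Nothing in the documents mentions tilt or uterine displacement, recording of the position used, or a cut-off specific to pregnancy or position. Section 10 does not mention the cardiac outcome.

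**The concern.** A supine woman with a gravid uterus can have her great veins compressed, which reduces venous return and so the cardiac output that is measured. This is general physiology, not something the documents state, and it is put here as a possibility. It acts while the woman is pregnant and is taken to be absent at the after-delivery scan. Using the same position at both scans therefore does not cancel it, because delivery removes the cause.

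With a single absolute cut-off, a downward shift in measured CI becomes misclassification in one direction only: some women with a true CI above 2.5 are counted as abnormal. If the reported frequency uses the pre-delivery scan, or counts low CI at either scan, it can be too high. If it pools whichever scan is available, it combines readings open to the effect with readings that are not, in proportions set by late arrival, emergencies and postpartum onset. The result would be hard to interpret or to compare with other cohorts.

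**Working it through.** **What the text settles.** Putting sections 5, 7.4.3 and 8.1.2 together, the planned pre-delivery echocardiogram is acquired supine. Sections 4 and 6.4 apply CI <2.5 without a time point. No section offsets the effect by tilt, by recording position or by splitting the result. The direction of any error follows from this; the size does not.

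**What is missing.** The documents give no expected frequency of low CI, no mean or SD of CI, no positional effect, no gestational age limit and no sample size (all eligible patients over 12 months). There is no plan figure to reproduce, and what follows is an illustration.

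**Inputs**
- Cut-off: 2.5 l/min/m2 (section 6.4).
- Assumed: true CI is normal with mean m = 3.5 and SD s = 0.7 or 0.8.
- Assumed: supine position lowers measured CI by a fraction f = 0.10 or 0.20.
- Assumed: a share a of women is affected, 30% or 100%.

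**Step 1: effective cut-off.** An affected woman is classed as abnormal when (1 − f) × true CI < 2.5, that is, when true CI < 2.5/(1 − f).
- f = 0.10: 2.5/0.90 = 2.78
- f = 0.20: 2.5/0.80 = 3.125

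**Step 2: share classed as abnormal if affected.** With Φ the standard normal distribution function, p0 = Φ((2.5 − m)/s) and p1 = Φ((2.5/(1 − f) − m)/s).

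| SD | No effect | 10% fall | 20% fall |
|---|---|---|---|
| 0.7 | Φ(−1.43) = 7.7% | Φ(−1.03) = 15.1% | Φ(−0.54) = 29.6% |
| 0.8 | Φ(−1.25) = 10.6% | Φ(−0.90) = 18.3% | Φ(−0.47) = 32.0% |

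**Step 3: only some women affected.** The share is p0 + a(p1 − p0). With a = 0.30 and SD 0.7:
- 10% fall: 7.66 + 0.30 × (15.11 − 7.66) = 9.9%
- 20% fall: 7.66 + 0.30 × (29.61 − 7.66) = 14.2%

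**Step 4: sensitivity to the assumed distribution, all women affected.** For falls of 0, 10 and 20%:
- mean 4.0, SD 0.8: 3.0%, 6.3%, 13.7%
- mean 3.0, SD 0.6: 20.2%, 35.6%, 58.3%

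**Step 5: pooling.** If a fraction w of the counted scans is from before delivery, the pooled frequency is w × p(before) + (1 − w) × p(after). The plan gives no w. Two cohorts with identical cardiac function would report different frequencies if they differed only in how many women arrived in time for the first scan.

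**The case against.** The strongest reply is that the plan never says the pre-delivery scan is the one counted. If the outcome were taken after delivery, the bias would not arise, and on this view the real gap is only the unnamed time point. That limits the claim: the inflation is conditional. It does not remove it, because an unnamed time point leaves the analyst free to count the affected scan, either scan, or a mixture.

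A second reply is that the magnitude rests wholly on assumptions and that not every woman need be affected. This stands. The inclusion criterion gives no gestational age, the all-affected scenario is an upper case, and women scanned only after delivery would dilute a pooled figure. The 30%-affected scenario is shown for that reason.

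A third reply is that this is one secondary outcome in a study the plan itself calls exploratory and descriptive. This is true, and the primary lung ultrasound endpoints do not depend on CI.

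Four stronger readings may tempt a reader, and the documents support none of them.
- *The before-after change in CI is biased toward recovery.* The plan names no such endpoint; its only delta is for the lung ultrasound score.
- *False low readings would move women out of the ARDS category.* Table 1 does not use CI <2.5. It asks for an objective assessment, with echocardiography as an example, only when no risk factor is present, and contractility is assessed as well as output.
- *The inferior vena cava scan is affected too.* It appears in the synopsis as a procedure, but no outcome, definition or analysis uses it.
- *The position strains the patient.* Supine does not fix head elevation, lung ultrasound is also done supine under section 8.1.1, and the measurement argument does not need this point.

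**Conclusion.** The point holds as a conditional measurement problem. Following the plan as written can produce position-related low-CI readings in women scanned before delivery, and nothing in the plan would let a reader detect or separate them. The direction is upward for any frequency that uses those scans.

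The size cannot be derived from the documents. With an assumed mean CI of 3.5 and a 10-20% fall, the abnormal share goes from about 8% to 10-14% if 30% of women are affected (SD 0.7), and from 11% to 18-32% if all are (SD 0.8). These figures also rest on a normal distribution and a proportional fall of the same size in each affected woman. They show that the effect could matter, not that it will have a given size. Reading the first time point as the pre-delivery scan is an inference from section 5, since T1 and T2 are named but not defined.

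A change is worthwhile because it is cheap. The concern is confined to one secondary outcome.

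**What to change.** 1. In section 8.1.2, replace the supine instruction for the echocardiogram with one left-tilted acquisition position, the same before and after delivery, where feasible.
2. Add a CRF field for the position actually used at each scan.
3. In sections 4 and 10, report the CI <2.5 proportion separately before and after delivery, each with its own denominator, and do not pool the two.
4. Show the pre-delivery proportion by recorded position as a descriptive check only. Women who could not be tilted may be sicker, so a difference between positions would mix position with severity and should not be read as a correction.

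The cost is one sentence, one tick box and one table split, with no added procedure. The downside is that some women cannot be tilted; their scans are kept and flagged. If scanning is already complete, step 3 can still be done without new data.

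This concerns only how the study image is acquired and reported, not patient management.

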10. STATISTICS AND ANALYSIS

For descriptive purposes continuous and ordinal variables data will be expressed as median with interquartile range. For categorical variables, percentages are calculated. Student's t-test or analysis of

variance (ANOVA) will be used to compare normally distributed numerical variables. Mann Whitney Utests and Kruskal-Wallis tests will be used to compare numerical variables when normality cannot be assumed, while chi-squared tests will be used to compare categorical variables. Univariate logistic regression analyses will be performed to identify potential factors associated with the clinical outcomes including, but not limited to, presence of interstitial syndrome, non-resolution of interstitial syndrome at 48-72h, development of ARDS and death in hospital. Multivariable logistic regression models will be used to identify independent risk factors for the same clinical outcomes. A forward and backwards stepwise approach will used to include variables into the models, with a limit of P <0.2.

Inter– observer variability of the lung ultrasound score between the study sonographer and an independent expert will be calculated on a random sample of 10 cases (120 lung regions) using Cohen K-statistics. Statistical analyses will be conducted using R (www.r-project.org). A P-value of <0.05 will be considered statistically significant. Analyses will be conducted after the end of patient recruitment and no interim analyses are planned. Statistical analysis will be performed with R software (R Foundation for Statistical Computing, Vienna, Austria).

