1. SYNOPSIS

Study Title	SeveriTy of Pulmonary Edema and timing of Resolution in patients with severe pre-eclampsia and eclampsia (TIPER) – a prospective observational study		
Internal ref. no. (short title)	Pulmonary edema resolution in severe pre-eclampsia and eclampsia – TIPER		
Study Design	A prospective, observational cohort st	udy.	
Study Participants	Female subjects, hospitalized with seven	ere preeclampsia or eclampsia	
Planned Sample Size	All eligible patients admitted to PCMH for 1 year		
Study Site	Princess Christian Maternity Hospital,	Freetown, Sierra Leone	
Planned Study Period	April 2023 to April 2024.		
Inclusion criteria	All patients with severe pre-eclampsia during the study period	or eclampsia admitted to hospital PCMH	
Exclusion criteria	 Patients with chronic hypertensive disorders Lung ultrasound not feasible, e.g., due to electricity breakdown, or absence of the trained sonographer or presence of subcutaneous emphysema, 		
Aim	The primary aim is to describe the frequency of lung ultrasound consistent with pulmonary oedema and the timing of resolution after delivery. Secondary aims include the assessment of the frequency of acute respiratory		
	failure, other LUS findings beyond pulmonary edema, the assessment of oxygenation, the use of respiratory organ support strategies, assessment of cardiac function, and quantification of major direct/ indirect obstetric complications and of perinatal complications.		
Hypothesis	 A high proportion (>20%) of patients show LUS signs consistent with pulmonary edema before delivery. There is incomplete resolution of both clinical and ultrasound signs of pulmonary edema 48 hours after delivery. 		
	Objectives	Outcome Measures	
Primary	Frequency of LUS consistent with pulmonary edema	Frequency endpoint: proportion of patients with a LUS positive for pulmonary edema Severity: LUS areation score	
	Timing of resolution after delivery	Categorical: Fraction of patients with improvement or resolution of LUS findings. Numerical: delta LUS score between T1 and T2	
Secondary	Frequency of acute respiratory failure in patients with Severe Pre eclampsia and in patients with Eclampsia	Proportion of patients with acute respiratory failure	

	Frequency of other LUS findings	 Proportion of patients with consolidations isolated pleural effusion 	
		minor LUS findings	
	Frequency of organ support strategies	Fraction of patients that receive oxygen and/or CPAP and/or mechanical ventilation	

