4.1 Hypothesis

- 1. A high proportion (>20%) of patients show LUS signs consistent with pulmonary edema before delivery.
- 2. There is a resolution of both clinical and ultrasound signs after in the 48 hours after delivery.

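### If the T1–T2 change in LUS score is tested, Section 10 names no paired test for non-normal or categorical data

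*Combined protocol and SAP*

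**What the plan says.** Section 4 and the synopsis place the change over time under the primary objective, "To describe the timing and entity of edema resolution after delivery". It has two outcome measures: the share of women whose LUS findings improve or resolve, and "Quantitative endpoint: delta LUS score between T1 and T2". T1 and T2 are not defined by name. I read them as the two examinations in Section 5, one before delivery and one 24 to 72 hours after it, in the same woman. Section 5 also allows some women to have the post-delivery examination only.

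Section 10 summarises continuous and ordinal variables by median and interquartile range. For normally distributed data it names Student's t-test or ANOVA, without saying whether the t-test is paired. Otherwise, "Mann Whitney Utests and Kruskal-Wallis tests will be used to compare numerical variables when normality cannot be assumed", and "chi-squared tests will be used to compare categorical variables". It adds "A P-value of <0.05 will be considered statistically significant". It also plans logistic regression for per-woman outcomes, including "non-resolution of interstitial syndrome at 48-72h". No signed-rank test, McNemar test, repeated-measures model or mixed model appears anywhere in the document.

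**The concern.** Mann-Whitney, Kruskal-Wallis and chi-squared tests assume that the observations compared come from different people. T1 and T2 scores come from the same people. An analyst who applies Section 10 as written to the two columns of scores would use a standard error, or its rank equivalent, that leaves out the within-woman correlation.

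This is a foreseeable step. The global LUS score is a bounded sum of ordinal grades, 0 to 36 (Sections 6.4 and 8.1.1), so the non-normal rule is the likely one. The protocol states hypotheses about resolution after delivery and sets a significance threshold. At stake is the P value attached to a primary endpoint, and a choice of test left open until the data are seen.

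**Working it through.** **Figures in the plan.** There is none to reproduce. The document gives no number of pairs, standard deviation, effect size, T1–T2 correlation or oedema frequency at either time. Section 5.1 (sample size) says only that all eligible patients over 12 months will be recruited. Everything below except the 0.05 threshold and the 0–36 range is an assumption, and the test is taken as two-sided.

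**True size of an unpaired test on paired data.** With equal variances σ², n pairs and correlation r:

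- variance assumed by the unpaired test for the difference in means: 2σ²/n
- actual variance: 2σ²(1 − r)/n
- the standard error is therefore overstated by 1/√(1 − r), and the true size is 2 × [1 − Φ(1.960/√(1 − r))]

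| r | 1.960/√(1 − r) | SE overstated by | True size |
|---|---|---|---|
| 0 | 1.960 | 1.00 | 5.0% |
| 0.3 | 2.343 | 1.20 | 1.9% |
| 0.5 | 2.772 | 1.41 | 0.6% |
| 0.7 | 3.578 | 1.83 | 0.04% |

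At r = −0.3 the same formula gives 8.6%, so the error would reverse. Nothing in the documents suggests a negative correlation.

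**Size by simulation, no true change.** With 50 pairs of skewed integer scores from 0 to 36 (gamma margins, normal copula, 2,000 replicates), Mann-Whitney rejects in 5.3%, 2.5%, 0.8% and 0.05% of replicates at latent r = 0, 0.3, 0.5 and 0.7. The signed-rank test stays between 4.8% and 5.5%.

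**Power by simulation, Mann-Whitney versus signed-rank.** The first row uses the model above with T2 scores 25% lower. The others use negative binomial margins (dispersion 3, capped at 36), a Gaussian copula and 4,000 replicates.

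| Scenario | r = 0 | r = 0.3 | r = 0.5 | r = 0.7 |
|---|---|---|---|---|
| 50 pairs, 25% lower | 27.4% v 30.2% | 24.1% v 40.3% | 20.9% v 50.7% | 16.8% v 73.0% |
| 60 pairs, mean 8 to 6 | 56.6% v 58.7% | 57.1% v 72.9% | 57.5% v 85.4% | not run |
| 150 pairs, mean 8 to 6 | 92.5% v 93.6% | 95.3% v 98.7% | 97.0% v 99.6% | not run |
| 200 pairs, mean 8 to 6 | not run | 99.2% v 99.9% | 99.7% v 100% | not run |
| 60 pairs, mean 8 to 4 | not run | 99.9% v 100% | 100% v 100% | not run |

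The loss is negligible with no correlation, many pairs or a large change. It is large with few pairs, a modest change and high correlation: at 50 pairs and r = 0.7 it is 73.0 − 16.8 = 56.2 percentage points. These are examples, not bounds.

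**Categorical data, if oedema status at T1 and T2 were compared.** Chi-squared versus McNemar, without continuity correction, 20,000 replicates: 60 women, 30% falling to 15%, 50.6% v 64.6% at phi = 0.3 and 51.3% v 80.4% at phi = 0.5; 200 women, 30% falling to 20%, 66.6% v 79.0% and 69.7% v 91.4%.

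**The case against.** The strongest reply is that no unpaired T1–T2 test is planned. Section 10 lists general tests and assigns none to this comparison. The endpoint is the change itself, one value per woman, and a median with interquartile range already respects the pairing. The other resolution endpoint is a simple proportion, non-resolution is modelled per woman, and Mann-Whitney is a proper test for comparing the change between severe pre-eclampsia and eclampsia. The objective is descriptive. The synopsis hypothesis ("There is incomplete resolution of both clinical and ultrasound signs of pulmonary edema 48 hours after delivery") and the Section 4.1 hypothesis ("There is a resolution of both clinical and ultrasound signs after in the 48 hours after delivery") point in different directions, but both ask whether signs resolve, which a proportion with an interval answers better than a test of zero change.

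All of that stands, and it makes the point conditional. It does not remove it: Section 10 states its rules without restriction, so a T1–T2 P value, if one is produced, is directed to the wrong test.

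A reader might infer more than the documents support in four ways:

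- That the plan prescribes an invalid primary analysis. It does not; it omits a valid test.
- That every route is unpaired. On the normal-data route, a paired t-test is compatible with the text.
- That false positive findings would result. With positive correlation the error runs the other way.
- That McNemar's test is missing for a listed endpoint. No listed endpoint compares oedema prevalence at T1 with that at T2.

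**Conclusion.** The point holds as a conditional omission on a primary endpoint. If T1 and T2 are compared under the non-normal or categorical rule of Section 10, the P value is wrong. With positive within-woman correlation the test is conservative, with a true size of about 1.9% at r = 0.3 and 0.6% at r = 0.5 in place of 5%, and it loses power. The size of the power loss cannot be fixed from the documents; in the assumed scenarios it runs from almost none to more than 50 percentage points.

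This rests on reading T1 and T2 as the pre- and post-delivery scans, on a two-sided test and on positive correlation. The descriptive and between-group analyses need no change on this account. Section 10 should be amended because a better method is available at almost no cost.

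**What to change.** Add to Section 10:

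1. The T1–T2 change in LUS score is estimated with a 95% CI and, if tested, uses the Wilcoxon signed-rank test, or the paired t-test if the differences are normal.
2. Mann-Whitney, Kruskal-Wallis and chi-squared tests are for comparisons between groups of different patients, including comparisons of the change between severe pre-eclampsia and eclampsia.
3. The number of women with both scans is reported with every T1–T2 result.
4. Optionally, McNemar's test is used if oedema status at T1 and T2 is compared.

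The cost is a few sentences and no new data. The downside is that a paired analysis uses only women with both scans. Because Section 5 permits a post-delivery scan alone after late arrival, in an emergency or with postpartum onset, these women may not represent the whole cohort. Item 3 lets the reader see how many are left out.
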